## **9.5 Safety analysis**

To assess safety, vital signs will be monitored daily and we will also monitor the frequency abnormal lab values as well as adverse and serious adverse events during period of active intervention as well as throughout the subjects' participation in the study. To assess the side effect profile of Losartan in this population, we will monitor the frequency of subject complaints, symptoms (dizziness, new fatigue, peripheral edema, urinary symptoms) and laboratory measures of liver and renal function, hemoglobin and hematocrit counts and serum potassium and uric acid levels. The frequency of abnormal lab values, adverse and serious adverse events and side effects will be monitored separately for the Losartan and placebo control groups. Differences between groups will be assessed using Fisher exact tests.

Any deviations from the previously described statistical plan will be described and justified in a protocol amendment and/or in the final report submitted to the IND application.

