In conducting this phase 1 study, we will utilize the multidisciplinary collaboration of an experienced group of scientists, surgeons and physical therapists in a unique environment at the University of Pittsburgh and the USAISR (United States Army Institute of Surgical Research) at Brooke Army Medical Center (BAMC) San Antonio, Texas. The main outcome measures will be to (a) quantify the length and volume of fibrosis in the injured hamstring muscle, based on a baseline 3 Tesla MRI and a subsequent follow-up MRI examination 6 months post-injury and (b) prospectively follow the subjects to evaluate the amount of scarring and time to return to prior activity. Safety and tolerability will be assessed by monitoring adverse events, symptoms (dizziness, new fatigue, peripheral edema or urinary symptoms), hypotension, and laboratory measures of liver and renal function, hemoglobin and hematocrit counts and serum potassium and uric acid levels.

A 1999 study in the United Kingdom^67 examined the safety of losartan potassium post-marketing in over 14,000 patients. The results of this study indicate losartan potassium, like other angiotensin II receptor antagonists (ARBs), does not present any significant adverse events. The most commonly cited specific adverse events include dizziness, headache, malaise, nausea, lassitude, cough, diarrhea, dyspnea and impotence. A literature review conducted by Sica *et al.* found other adverse events being decreases in hemoglobin and hematocrit counts, dysgeusia and ageusia, migraines and acute psychosis, hepatic abnormalities, angioedema, increase in serum potassium, decrease in serum uric acid, and changes in renal function. As is the case with all drugs directly affecting the renin-angiotensin system, Losartan should not be taken by anyone who is pregnant or thinks they may be pregnant. The use of these drugs can cause neonatal injury, hypotension, neonatal skull hypoplasia, anuria, renal failure and death. To our knowledge losartan potassium has not been withdrawn from research or marketing in the United States or any other country.

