#### **3.1 Study design schematic**

After signed informed consent is provided, subjects will undergo screening that will include collection of baseline demographics, medical history, activity level, baseline vital signs (blood pressure and heart rate), blood tests including a chemistry panel with electrolytes and complete blood cell count (CBC), pregnancy test for women, physical examination, measurements of pain and hamstring flexibility and strength and a 3.0 Tesla MRI. After screening to confirm eligibility, subjects will be randomized to receive Losartan or placebo for four weeks. All subjects will undergo standard of care rehabilitation. During the period of active intervention, subjects will be followed weekly. Blood work will be repeated 2, 4, and 6 weeks after randomization. Pregnancy tests for females will also be repeated 2, 4, and 6 weeks after randomization. Throughout the remainder of the year-long study period, subjects will undergo follow-up testing at 6 and 12 weeks, 4, 6, 9 and 12 months. The study procedures over time are summarized in the table (**Table 1**) below.

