## **5. Study Drug(s):**

As described in section 1.2, losartan potassium is an FDA-approved drug for the treatment of hypertension, left ventricular hypertrophy and diabetic nephropathy. It is prescribed for oral intake at doses from 25-100 mg per day with a usual starting dose of 50 mg per day which is what will be used for this study. Losartan potassium was developed by Merck under the proprietary name Cozaar® and is now generically available.

Prior to starting the study medication, a study physician will review the effects of losartan, its side-effects and how the medication should be taken with all subjects. At this time, the physician will answer any questions the subject has regarding the study medication. Subjects will be evaluated weekly while they are taking the medication. Blood work will be repeated 2, 4 and 6 weeks after randomization to identify any clinically relevant abnormalities.

Following randomization, subjects will begin a closed label course of 50mg of Losartan daily for 4 weeks or placebo for the same duration of time. Losartan will be initiated within 7 days of injury after initial tests are performed and any abnormalities are ruled out. No initial dosage adjustment is necessary. The drug will be self-administered by the subject with or without food and will be ingested once a day. With the dose that will be used in this study, no tapering is necessary at the end of the intervention phase or if the subject needs to be withdrawn from the study.

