#### **6.3.4 Blood Draw Procedures**

For the blood draws, the subject will be comfortably seated and identification of the subject will be confirmed. Blood will be drawn from the median cubital vein. Initially a tourniquet will be placed on the arm, proximal to the location where the blood will be drawn. The skin around this area will be wiped with an alcohol swab (or iodine prep). A needle will be inserted, bevel facing upwards, into the median cubital vein. Once the needle is in the vein, a vacutainer is pushed onto the needle holder and this will be repeated until all blood samples required are completed. Once the needle is removed, clean cotton wool will be pressed onto the wound. The tubes will be labeled immediately. Sufficient blood will be drawn to permit a chemistry panel with electrolytes and CBC. Hemoglobin and hematocrit counts, serum potassium and uric acid, liver function (alanine aminotransferase (ALT), aspartate aminotransferase (AST) and alkaline phosphatase), renal function (blood urea nitrogen [BUN] and serum creatinine), creatine phosphokinase (CPK) to assess muscle injury, and pregnancy in women (human chorionic gonadotropin (hCG)) will be assessed.

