## 9.

## **Statistical Methods/Data Analysis:**

### **9.1 Study endpoints**

#### **9.1.1 Primary endpoint(s)**

**Specific Aim #1: To determine safety and tolerability of Losartan when used for treatment of an acute grade II or III hamstring strain.**

To assess safety, vital signs will be monitored daily and we will also monitor the frequency of abnormal lab values as well as adverse and serious adverse events during period of active intervention as well as throughout the subjects' participation in the study. To assess the side effect profile of Losartan in this population, we will monitor the frequency of subject complaints, symptoms (dizziness, new fatigue, peripheral edema, urinary symptoms) and laboratory measures of liver and renal function, haemoglobin and haematocrit counts and serum potassium and uric acid levels. The frequency of abnormal lab values, adverse and serious adverse events and side effects will be monitored separately for the Losartan and placebo control groups.

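### Laboratory safety is compared between arms only as counts of abnormal values, which is insensitive to the shifts in level expected from losartan and does not estimate their size

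*Combined protocol and SAP*

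**What the plan says.** Section 9.1.1, under Specific Aim 1, sets the laboratory endpoint: "we will also monitor the frequency of abnormal lab values as well as adverse and serious adverse events". Section 9.5 repeats it by arm ("The frequency of abnormal lab values, adverse and serious adverse events and side effects will be monitored separately") and adds the test: "Differences between groups will be assessed using Fisher exact tests". It also lists, for the side-effect profile, "laboratory measures of liver and renal function, hemoglobin and hematocrit counts and serum potassium and uric acid levels". Neither section asks for a mean, a change from baseline, a shift table or a baseline-adjusted difference. Neither says what makes a value abnormal for analysis.

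Four other places bear on this:

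- Section 1.2 reports from the literature reduced haemoglobin and haematocrit, and "increase in serum potassium, decrease in serum uric acid, and changes in renal function".
- Sections 4.1 and 4.2 restrict entry to ages 18-35 and exclude diabetes and cardiovascular, renal or hepatic disease. Section 5 starts dosing only "after initial tests are performed and any abnormalities are ruled out".
- Section 3.1 schedules the samples: "Blood work will be repeated 2, 4, and 6 weeks after randomization". A pre-randomization sample is also taken, and section 5 sets the course at 4 weeks.
- Sections 6.3.4 and 7.2 name the individual tests, including creatinine, BUN, ALT, AST and alkaline phosphatase. They also include "creatine phosphokinase (CPK) to assess muscle injury".

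**The concern.** The effects cited in section 1.2 are changes in the level of continuous measurements, most with a stated direction. Someone who starts mid-range and moves moderately in that direction is still normal and adds nothing to the count. Selecting young adults without relevant disease, and checking them before dosing, makes this the usual case.

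Hypothesis 1b is that the side-effect profile is comparable to placebo, judged partly on laboratory values. A count with little sensitivity can appear to support that hypothesis even when mean potassium or haemoglobin has moved. Section 9.2 says the trial cannot rely on significance and should estimate effect sizes for later trials. A proportion outside a limit does not give the size or spread of a shift, although the samples needed to estimate both are already drawn.

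**Working it through.** **The plan's own figure.** There is nothing to reproduce. Section 9.2 gives 20 subjects (10 per group) as an approved number, with no effect size, SD or power. No significance level is stated, so I take two-sided 5%.

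**What the Fisher test needs at 10 v 10.** For k abnormal on losartan and none on placebo, p = 2 × C(10,k) / C(20,k).

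- k = 4: 2 × 210 / 4845 = 0.087.
- k = 5: 2 × 252 / 15504 = 0.033.

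Five against none is the smallest split that reaches 5%. With one abnormal value on placebo, seven are needed on losartan (p = 0.020; 6 v 1 gives 0.057).

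**Assumptions for the illustration (none from the documents).** One analyte, one visit, normal values, reference limit at 1.96 SD, true shift d in SD units on losartan and zero on placebo, correlation r between baseline and follow-up.

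**Formulas.**

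- Share beyond the limit: 1 − Φ(1.96 − d). This is 2.5% for d = 0, 7.2% for d = 0.5 and 16.9% for d = 1.
- Fisher power: exact enumeration over both binomials. Check for d = 1: P(at least 5 of 10 at 16.9%) is about 0.0164 and P(0 of 10 at 2.5%) is 0.776. Their product is about 0.013.
- Continuous, unadjusted: t test on 18 df, noncentrality d / √(2/10). For d = 1 this is 2.24.
- Baseline-adjusted: approximately 17 df, noncentrality d / (√(1 − r²) × √(2/10)). For d = 1 this is 2.58 at r = 0.5 and 3.13 at r = 0.7.

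| True shift | Beyond limit, losartan v placebo | Fisher power | Continuous | Baseline-adjusted, r = 0.5 to 0.7 |
|---|---|---|---|---|
| 0.5 SD | 7.2% v 2.5% | 0.03% | 19% | 23-32% |
| 1 SD | 16.9% v 2.5% | 1.3% | 56% | 68-84% |

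**A reading kinder to the plan.** Count a subject as abnormal if the value passes the limit in the expected direction at any of the three post-randomization visits. Assume baseline in range and correlation 0.5-0.8. A 1 SD shift then makes 26-33% of losartan subjects abnormal against 3-6% on placebo, and Fisher power is 6-13%. This also assumes the full shift persists at week 6, about 2 weeks after the 4-week course ends.

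**Precision of the alternative.** The 95% half-width for the baseline-adjusted difference is 2.11 × √(1 − r²) × √(2/10). This is 0.82 SD at r = 0.5 and 0.67 SD at r = 0.7.

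**The case against.** The strongest reply is that section 5 gives the repeat blood work a clinical purpose, finding relevant abnormalities, and counting abnormal values serves it. Sections 2.1 and 3 state two purposes. Safety is to be judged by adverse events and tolerability, and the effect of losartan by muscle, return-to-sport and recurrence outcomes. Section 9.2 also disclaims power for clinical measures. All of this stands, and it would be wrong to say that estimating magnitude is the trial's only purpose. It does not remove the gap. Section 9.5 does compare the arms on laboratory values, and an estimate with an interval is useful where a test is not.

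A second reply is that section 9.4 promises mixed models for repeatedly measured outcomes and lists safety among the primary outcomes. That sentence falls under effectiveness and names no laboratory value, and 9.5 specifies frequencies and Fisher tests. The list of laboratory measures in 9.5 could be read as monitoring the values themselves, but no summary of them is given.

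A reader might infer more than the documents support:

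- **That shifts would go unseen, or counts would be near zero.** With a 1 SD shift, the chance of at least one abnormal losartan subject among 10 at one visit is 1 − 0.831^10 = 84%. Over three visits it is 95-98%. At 1.5 SD, Fisher power is about 15% at one visit and 41-54% over three. Sections 8.2.2 to 8.2.2.2 have abnormal findings recorded and reviewed individually.
- **That injury-driven CPK flags will inflate the count.** The analyte lists in 9.1.1 and 9.5 omit CPK. Because CPK is in the safety blood work of 7.2 and the phrase about abnormal values is unqualified, the point needs a clarifying sentence only.
- **That the sites use different reference ranges.** The only support is a generic record-retention list in section 11.2, which does not say that the ranges differ.
- **That on-drug and off-drug periods are not distinguished at all.** Sections 9.1.1 and 9.5 mention the active intervention period alongside whole participation. They do not say that week 6 laboratory results will be tabulated separately.

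**Conclusion.** The point holds as a weakness of analysis, not of data collection. The only between-arm laboratory comparison specified is a count of abnormal values. At 10 per arm this is insensitive to moderate shifts and does not estimate their size or variability. For a 1 SD shift the illustration gives power of about 1% (6-13% over three visits), against 56% for the same values kept continuous and 68-84% after baseline adjustment. These figures rest on assumed normality, a limit at 1.96 SD, assumed correlations and assumed shift sizes, because the documents give no SDs, limits or expected changes. The ordering of the methods matters more than the exact percentages.

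The stronger claim, that real laboratory effects would be missed altogether, is not supported: large shifts would push some subjects out of range, and individual abnormal values are reviewed. The change is worth making because it serves the primary aim and uses samples already scheduled.

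**What to change.** In section 9.5:

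- For haemoglobin, haematocrit, potassium, uric acid, creatinine, BUN, ALT, AST and alkaline phosphatase (the tests named in 6.3.4 and 7.2), report the between-arm difference at weeks 2 and 4, adjusted for the baseline value, with a 95% confidence interval. Describe this as estimation.
- Show week 6 separately, as the sample taken about 2 weeks after the 4-week course ends.
- Keep the abnormal counts by arm as a supplement, with a definition of abnormal.
- State that CPK is reported separately as a muscle-injury marker.

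The cost is a few sentences and one extra table. No new samples or visits are needed, and clinical management is unchanged. The downside is a set of descriptive intervals without multiplicity control, which is acceptable in a pilot if they are labelled as such.

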#### **Specific Aim #1: To determine safety and tolerability of Losartan when used for treatment of an acute grade II or III hamstring strain.**

*Hypothesis 1a:* Use of Losartan will have an acceptable adverse event profile that is comparable to placebo. To test this hypothesis we will monitor adverse and serious adverse events throughout the duration of the study.

*Hypothesis 1b:* The side effect profile of Losartan will be comparable to placebo. To test this hypothesis we will monitor subject complaints, symptoms, hypotension, and laboratory values.

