The severity of an adverse event will be determined by the study medical director based on the criteria stated in section 8.1. Additionally, the medical director will assign the event a grade of mild, moderate, or severe. If it becomes medically necessary to withdraw the subject from the study, the study medication will be discontinued. The subject will be followed clinically until the adverse event or abnormal test findings felt to be associated with the study drug resolves or stabilizes at a level acceptable to the Sponsor-Investigator. This follow-up will include assessment of vital signs, physical examination and assessment of blood work. Follow-up blood work will be performed 4-6 weeks ( $\pm 3$  days) after discontinuing medication to ensure that lab values have returned to normal ranges after discontinuation of the study medication. The subject will be treated for any medication related problems as clinically appropriate. Information from this appointment will be documented in the subject's case file. The patient will be terminated from the study, and will not complete any further follow-up appointments for the study. Subjects that are terminated from participation in the study due to an adverse event will be replaced by recruitment of another subject.

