## **9.2        Sample size determination**

With an approved sample size of 20 patients (10 in each group), we will not have enough statistical power to detect statistically significant differences in clinical measures between the Losartan and placebo groups. Therefore the objective of this phase 1 trial is to observe trends by group and estimate effect sizes that can be used to inform power calculations in future clinical trials.

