## **9.3        Definition(s): Analysis population(s)**

All analyses for treatment group comparisons will use the original treatment assignment as randomized for each participant (intent-to-treat) regardless of the subject's actual compliance with taking the study medications. Secondary analyses will consider per protocol analysis, in which compliance with the study medication regimen will be defined as taking greater than 80% of the doses.

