### **13. Study Discontinuation Criteria:**

#### **13.1 Discontinuation of individual research subjects (refer also to sections 5.1.1 and 8.4)**

Because we are interested in evaluating efficacy, we will use a per-protocol approach, as opposed to an intention-to-treat approach for the conduct of this study. As such, subjects that are non-compliant with the medication regimen (defined as taking less than 80% of the medication doses) will be withdrawn from the study and additional subjects will be recruited to replace subjects that have been withdrawn due to non-compliance. Subjects that are withdrawn for non-compliance will be instructed to terminate administration of the study medication without tapering down the dose and to return unused medication to the investigators.

As specified in section 8.4 subjects with symptomatic hypotension or abnormal lab values will be withdrawn from study participation. Additionally, females that become pregnant while taking the study medication will immediately stop the medication and will be withdrawn from the study. These withdrawn subjects will be followed clinically based on standards of care until the adverse event or abnormal test findings felt to be associated with the study drug resolve or stabilize at a level satisfactory to the Sponsor-Investigator, however no further research data will be collected once the subject has been withdrawn.

Subjects that are withdrawn due to non-compliance with the study medication, symptomatic hypotension, abnormal lab values or pregnancy will be reported as an adverse event. Withdrawn subjects will be replaced by recruiting another subject to take the place of the withdrawn subject.

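### Aim 1 expects a safety profile comparable to placebo, but section 9.5 plans only frequencies and Fisher tests for a difference, with no interval; at 10 per arm a non-significant test cannot support comparability

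*Combined protocol and SAP*

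**What the plan says.** - **Section 2.1, Specific Aim 1.** Hypothesis 1a: "Use of Losartan will have an acceptable adverse event profile that is comparable to placebo". Hypothesis 1b: "The side effect profile of Losartan will be comparable to placebo". Neither hypothesis defines comparable or gives a margin.
- **Section 9.5.** Frequencies of abnormal laboratory values, adverse events, serious adverse events and side effects are kept separately by arm. Then: "Differences between groups will be assessed using Fisher exact tests". Alpha, sidedness and expected event rates are not stated, and no interval is planned.
- **Section 9.2.** With 20 patients, 10 per group, "we will not have enough statistical power to detect statistically significant differences in clinical measures". It follows that "the objective of this phase 1 trial is to observe trends by group and estimate effect sizes".
- **Section 9.3.** "All analyses for treatment group comparisons will use the original treatment assignment as randomized for each participant", with per-protocol analysis as secondary. Sections 5.1.1 and 13.1 say the opposite: the study will use a per-protocol approach rather than intention-to-treat.
- **Withdrawal and replacement.** Section 8.4: "Subjects that are terminated from participation in the study due to an adverse event will be replaced by recruitment of another subject". Section 13.1: "Withdrawn subjects will be replaced by recruiting another subject to take the place of the withdrawn subject". Section 13.1 also says that no further research data are collected after withdrawal.

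**The concern.** A test for a difference answers a different question from the one in 1a and 1b. Failing to find a difference is evidence of similarity only if the test would probably have found a difference large enough to matter, and with 10 per arm it would not.

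Safety and tolerability are named in section 1.2 as part of the main goal and are listed first among the primary endpoints in 9.1.1. If the only inferential output for them is a Fisher p-value, the final report will not show how large an excess of events on losartan remains compatible with the data. A future trial would need that information from Aim 1, and it is the kind of result that 9.2 says this study is meant to produce.

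**Working it through.** The plan gives no power or sample-size calculation to reproduce: 20 is described as an approved number, without inputs.

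**Inputs**
- From the documents: 10 per arm (9.2), 1:1 allocation (3.2), Fisher exact test (9.5).
- Assumed, because not stated: two-sided alpha 0.05; true event rates of 10% on placebo and 30% to 60% on losartan; 12 per arm as an example of arms enlarged by replacement.

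**1. Which tables are significant at 10 per arm.** With equal arms the two-sided Fisher p is twice the hypergeometric tail.

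- 4 v 0: 2 × C(10,4) / C(20,4) = 2 × 210 / 4,845 = 0.087
- 5 v 0: 2 × 252 / 15,504 = 0.033
- 6 v 1: 2 × (210 × 10 + 120) / 77,520 = 4,440 / 77,520 = 0.057
- 7 v 1: 2 × (120 × 10 + 45) / 125,970 = 2,490 / 125,970 = 0.020

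With no placebo events, significance needs five on losartan. With one placebo event, it needs seven.

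**2. Exact power.** Power = Σ Bin(x; n, p₁) × Bin(y; n, p₀) over all tables with p ≤ 0.05, with p₀ = 10%.

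| Losartan rate | 10 per arm | 12 per arm |
|---|---|---|
| 30% | 6% | 9.5% |
| 40% | 15% | 23% |
| 50% | 30% | 42% |
| 60% | 47% | 64% |

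A three- to fourfold excess would usually be missed.

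**3. What a null result leaves open.** The Newcombe 95% interval for d = p̂₁ − p̂₀ combines the Wilson limits (l, u) of each arm:

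lower = d − √[(p̂₁ − l₁)² + (u₀ − p̂₀)²]; upper = d + √[(u₁ − p̂₁)² + (p̂₀ − l₀)²]

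- 1/10 v 1/10: Wilson limits 0.018 and 0.404. Half-width = √[(0.100 − 0.018)² + (0.404 − 0.100)²] = 0.315, so about -32 to +32 points, with Fisher p=1.0.
- 0/10 v 0/10: -28 to +28 points.
- 0/10 in a single arm: exact upper limit 1 − 0.025^(1/10) = 31%.

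**4. If replacement enlarges the arms (12 per arm).** 4 v 0 gives 2 × 495 / 10,626 = 0.093. 6 v 1 gives 2 × (924 × 12 + 792) / 346,104 = 0.069. 5 v 0 is again needed (p=0.037). 1/12 v 1/12 leaves -28 to +28 points, and 0/12 has an upper limit of 26%. The conclusion is unchanged.

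**5. Whether interval and test agree.** Near the boundary they often do not. The Newcombe interval excludes zero in all four non-significant unequal tables above:

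| Table | 10 per arm | 12 per arm |
|---|---|---|
| 4 v 0 | +4 to +69 | +2 to +61 |
| 6 v 1 | +8 to +75 | +5 to +67 |

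At 10% v 40% and 10 per arm, it excludes zero 29% of the time, against 15% for Fisher. Part of what Fisher misses is therefore due to its conservatism as well as to the sample size.

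**The case against.** The strongest reply is that the plan already concedes most of this. Section 9.2 admits low power for clinical measures and turns to estimation. Section 9.4, which counts safety and tolerance among the primary outcomes, says again that significance is not anticipated. In a phase 1 pilot, comparable may be an ordinary-language expectation and not a formal equivalence hypothesis. Frequencies by arm are point estimates, and a reader given counts and denominators can compute intervals. The mixed models in 9.4 might arguably extend to repeated laboratory values and vital signs, although they are placed under effectiveness.

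Much of that stands, and it lowers the severity. It does not supply the missing estimate: 9.5 has no step that matches the objective in 9.2. Leaving readers to compute intervals also leaves the method open, and the method can change whether zero is excluded.

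Three stronger readings are tempting, and the documents do not support them:
- **That the investigators will declare comparability from a non-significant test.** No section says so.
- **That low power is hidden.** Section 9.2 discloses it.
- **That subject protection depends on the Fisher test.** Section 13.2 has the monitoring committee weigh the number and severity of events against those expected with losartan, so the gap affects final reporting only.

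**Conclusion.** The mismatch holds. Hypotheses 1a and 1b concern similarity, the only safety inference planned in 9.5 is a test for a difference, and no safety interval is planned. At 10 per arm, a non-significant result is the likely outcome even when the true excess is 30 points (power 15% at 10% v 40%), and identical counts of one event per arm remain compatible with an excess of about 32 points.

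The power figures rest on assumed event rates and on two-sided alpha 0.05. Twelve per arm is also an assumption; the documents state only 10. Intervals would not establish comparability at this size. They would show what excess cannot be excluded. Severity is minor to moderate and limited to how Aim 1 is reported.

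**What to change.** **Hypotheses 1a and 1b.** Reword them as aims to estimate the losartan-minus-placebo difference in the proportion of subjects with an adverse event (1a), and with a complaint, symptom, hypotension or abnormal laboratory value (1b).

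**Section 9.5.** Add:

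> For each safety outcome, the proportion of subjects with an event will be reported by arm with an exact 95% CI, and the losartan-minus-placebo risk difference with a Newcombe 95% CI, among all randomized subjects, including those withdrawn and replaced. Aim 1 will be reported as the range of excess risk compatible with the data. Neither a non-significant Fisher test nor an interval that includes zero will be read as comparability. Fisher p-values are descriptive.

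Newcombe is one suitable choice; what matters is that the method is fixed in advance.

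**Withdrawals.** State that research data collection stops at withdrawal (13.1), so simple proportions may understate events in withdrawn subjects. Report the number withdrawn and the follow-up time by arm beside the proportions.

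**Analysis population.** Reconcile the per-protocol statements in 5.1.1 and 13.1 with 9.3, since the denominators above depend on it.

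**Cost.** A few sentences, with IRB approval of the modification as 13.2 requires. No new data or subjects are needed, no margin has to be set, and the Fisher tests can stay. There are two downsides. The intervals will be wide, so the safety statement will read less favourably. The Newcombe interval is also less conservative than Fisher and will often disagree with it near the boundary, so the text must say which one carries the interpretation.
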